Study Protocol and Statistical Analysis Plan

Title of Study: Pittsburgh and Rural Area High School Tobacco Prevention

ClinicalTrial.gov Identifier: NCT05081843

Principal Investigator: [name] [name], CHES

Date of Document: 3/16/2023

Table of Contents

	Page Number
Study Protocol	
Objectives.....	3
Design.....	3
Methods.....	3
Measures.....	4
Statistical Analysis Plan.....	6
Power and Sample Size.....	7

Study Protocol

Objectives:

Despite advances in tobacco control, tobacco use among adults continues to be a major clinical and public health challenge in the United States. This is exacerbated by the recent increase in adolescent overall tobacco use, likely prompted by the increased popularity of alternative tobacco products (ATPs) such as e-cigarettes. These products are marketed aggressively to adolescents online, and adolescents who engage with this marketing are more likely to initiate tobacco use. Considering adolescent tobacco initiation is associated with persistent nicotine addiction into adulthood, prevention efforts should be targeted at this population. Adolescent tobacco prevention programs that utilize a media literacy approach teach adolescents how to critically evaluate tobacco-related media messages. Designed for 9th grade students, the web-based media literacy program *AD IT UP* demonstrated initial feasibility and acceptability in 2011. In 2019, *AD IT UP* was updated to include ATPs and online tobacco marketing. However, the updated program has not yet been tested. The purpose of this study is to assess the feasibility and acceptability of the updated *AD IT UP* program among 9th grade students. We will conduct a cluster randomized trial comparing *AD IT UP* to usual substance use education in both high schools. Feasibility endpoints will assess completion of *AD IT UP* and associated assessments, while acceptability endpoints will assess student perceptions of *AD IT UP*. Secondary objectives are assess changes in intentions to use tobacco, attitudes, normative beliefs and tobacco media. Data collected from this study will inform a subsequent large-scale randomized controlled trial of *AD IT UP* to assess efficacy in decreasing tobacco initiation in high school students.

Design:

We will conduct a cluster randomized controlled trial (RCT) in two high schools in Pittsburgh, PA.

Methods:

[figure not shown]

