Sample and Recruitment. The two high schools will be selected according to the following criteria. Schools will have an adequate number of 9th-grade students (at least 130 at each school) to power this study. Each school must have at least 4 health classes to participate in the trial. One school will be located in a rural area and the other will be located in a suburban area. Parents will be sent a letter from the school informing them of the study aims and the procedure for opting out of consent. Student assent will be obtained before the all assessments. All assessments (intervention and control) and completion of *AD IT UP* (intervention) will be completed during regular class time in the school computer lab or on student devices (i.e., ChromeBook, iPad).

Randomization. Each school will have 4 health classes. Prior to the intervention (**Figure 2**), in each school, two classes will be randomized to the intervention condition and two classes to usual education using a random number generator

Pre-test Assessment and Assignment of Identifiers. In each school, all students (intervention and control) will be assigned a unique identifier and password, which will facilitate access to *AD IT UP* (intervention students), track progress through modules (intervention students), and link to the assessments (all students).

Intervention Condition. The intervention will be the updated *AD IT UP* web-based tobacco media literacy program. *AD IT UP* is self-paced and typically takes approximately 120 minutes to complete (including pre- and post-test assessments). In previous studies of the original *AD IT UP*, students completed *AD IT UP* over a series of 3 class periods delivered 1 week apart. **Figure 2** presents this scenario.

Figure 2. Overview of Study Procedures and Data Collection.

Control Condition. Many schools develop their own substance use prevention programming, so schools' usual programming will be used to mimic what is expected in a future trial. Students in the control condition will complete assessments on similar schedules as intervention students (**Figure 2**).

Post-test and Follow-up Assessments. Following the completion of the final *AD IT UP* module, all students will complete the post-test. Follow-up assessments will be completed at 4 and 12 months after the post-test (**Figure 2**).

Measures:

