• Tobacco-related media literacy	✓	✓	✓	✓		Norm Beliefs: 6 items with Likert scale (“Very Acceptable to Very Unacceptable) 8 items with Likert-type scale; (“SA” to “SD”)
Socio-demographic Factors						
• Age; Sex; Race/ethnicity	✓					Year; Male/Female/Other; Self-report

Statistical Analysis Plan:

Data will be analyzed using STATA.

Primary Outcome (feasibility): To answer the primary outcome of feasibility, we will calculate the number and percentage of students who completed each of the four assessments. We will answer the outcome of eligible students who participate we will calculate the number and percentage of students who were present in the classroom and (1) eligible (i.e., not opted out by parents) and (2) assent to participate (i.e., agree to participate by clicking “yes” on the assent form and completing the baseline assessment).

Acceptability: Acceptability will be assessed by calculating numbers and percentages for each of the seven overall program items. Acceptability is determined by answering “Agree” or “Strongly Agree.”

Secondary Outcomes: Although efficacy cannot be determined by a pilot trial, we will also assess changes in susceptibility, attitudes, normative beliefs, and tobacco media literacy using descriptive statistics and compare changes in these scores from pre to post-test and from post-test to follow-up between the intervention and control groups using two-sample tests of proportion. NOTE: Due to insufficient retention

of students for the 1-year follow-up assessments, changes in NTP susceptibility we assessed these changes between baseline and post-test assessments.

Power & Sample Size Justifications. Based upon a feasibility estimate of 60%, a sample size of 130 students (65 in each condition) in each school will afford the ability to estimate feasibility with a 95% confidence interval width of 0.17.

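### Health classes are randomised (8 in all), but the only between-arm test treats students as independent, so its p-values can be too small when change varies between classes

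*Combined protocol and SAP*

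**What the plan says.** The Design section states: "We will conduct a cluster randomized controlled trial (RCT) in two high schools". Under Methods, Randomization, "Each school will have 4 health classes", and within each school "two classes will be randomized to the intervention condition and two classes to usual education using a random number generator". The allocated unit is therefore the class: 2 schools × 4 classes = 8 classes, 4 per arm, balanced within school.

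The Secondary Outcomes paragraph of the Statistical Analysis Plan covers susceptibility, attitudes, normative beliefs and media literacy. It will "compare changes in these scores from pre to post-test and from post-test to follow-up" "between the intervention and control groups using two-sample tests of proportion". A NOTE in the same paragraph, citing poor retention at one year, says of the first outcome: "changes in NTP susceptibility we assessed these changes between baseline and post-test assessments".

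This is the only comparison between arms. Feasibility is a count and percentage, and acceptability is described in intervention students only. No section mentions an ICC, a design effect, a mixed or marginal model, cluster-robust errors or class-level summaries. The sample-size paragraph gives "a sample size of 130 students (65 in each condition) in each school" and applies no design effect.

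**The concern.** A two-sample test of proportion takes its standard error from variation between students. When classes are allocated, the arm difference also carries variation between classes, and only 4 classes per arm are available to average it out. If that component is left out, the standard error can be too small.

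The outcome is a change, so the component that matters is variation of the change between classes, for example through a shared teacher, peers or sessions. A stable difference in level between classes largely cancels from a change and need not inflate the error. Both programmes are delivered in class, so some class-to-class variation in change is plausible, but its size is unknown.

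At stake is how the secondary results are read. These data are meant to inform a larger trial, and a reader could see more evidence of a difference between arms than 8 randomised classes can give.

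**Working it through.** **Inputs from the documents.** 8 classes, 4 per arm; 130 students per school, 65 per condition. Mean class size m = 130/4 = 32.5.

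**Assumptions.** Two-sided 5% level; all 130 students per school analysed; the ICC values. The documents give none of these.

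**The plan's own figure.** The only stated precision is a 95% CI width of 0.17 at 60%. With n = 130, 2 × 1.96 × √(0.6 × 0.4/130) = 0.168. It reproduces, per school, with independent-student variance. It concerns a single proportion, so it says nothing about the comparison between arms.

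**Student-level test of change.** Design effect DEFF = 1 + (m − 1) × ICC of change. Actual error = 2 × [1 − Φ(1.96/√DEFF)]. Example at ICC 0.02: DEFF = 1 + 31.5 × 0.02 = 1.630, and the error is 12.5%.

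| ICC of change | DEFF | Actual error of a nominal 5% test |
|---|---|---|
| 0 | 1.000 | 5.0% |
| 0.005 | 1.158 | 6.8% |
| 0.01 | 1.315 | 8.7% |
| 0.02 | 1.630 | 12.5% |
| 0.05 | 2.575 | 22.2% |

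**From the ICC at one time point to the ICC of change.** Let r be the single-time ICC, c the pre-post correlation of class effects and k the pre-post correlation of students within class. Then ICC of change = r(1 − c)/[r(1 − c) + (1 − r)(1 − k)]. Assume r = 0.05 and k = 0.5:

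- c = 1 gives ICC of change 0 and error 5.0%.
- c = 0.9 gives 0.005/(0.005 + 0.475) = 0.010 and error 8.9%.
- c = 0.8 gives 0.010/(0.010 + 0.475) = 0.021 and error 12.7%.
- c = 0.5 gives 0.025/(0.025 + 0.475) = 0.050 and error 22.2%.

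**Simulation of binary susceptibility.** The plan does not say how a test of proportion is applied to changes, so three readings were simulated: mean student change; proportion of students improved; and difference in changes with pre and post treated as independent samples. Settings: 20,000 replicates, 2 schools, 2 classes per arm per school, 32 to 33 students per class, probit model with latent variance 1, 30% rate, stable student variance 0.5, no arm effect. Entries are rejection rates at nominal 5%.

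| Class variance: stable, class-by-time | ICC of change | Mean change | Improved | Pre/post independent | Class-level, 5 df |
|---|---|---|---|---|---|
| 0.10, 0 | 0 | 5.3% | 7.1% | 1.3% | 5.0% |
| 0.05, 0.01 | 0.009 | 8.3% | 8.0% | 2.9% | 4.9% |
| 0.05, 0.02 | 0.018 | 11.8% | 9.6% | 5.2% | 5.1% |
| 0.05, 0.05 | 0.045 | 21.3% | 16.5% | 12.3% | 5.0% |

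In the first row the single-time ICC is 0.058. A test of post-test levels alone would reject 25.2% of the time there, while the test of mean change stays near 5%. This shows how far a stable class effect cancels. The last column is a regression of the 8 class changes on arm and school. Over all 13 scenarios run it stayed between 4.8% and 5.3%.

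**The case against.** The strongest reply is that the largest figures belong to a test the plan does not name. The series up to 22.2% is for mean student-level change, whereas the plan names a test of proportions. The two readings that use proportions reach 16.5% and 12.3% at an ICC of change of about 0.045, and the one that treats pre and post as independent is below or near 5% up to about 0.018. This stands: even the direction of the error depends on a reading the plan leaves open. It limits what can be said about size but does not defend the test, since on none of these readings does the standard error reflect the allocation of classes.

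Other points also have weight:

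- The improved reading rejects 7.1% of the time with an ICC of mean change of 0, so for that reading a stable class difference is not wholly harmless.
- The program is web-based and self-paced, which makes a large ICC of change less obvious. The documents do not support 0.05 in particular, nor do they support zero.
- Analysed classes may be smaller than 32.5. At about 20 per class, the three readings give about 15%, 12% and 8% at an ICC of change of 0.045. Larger classes would raise the figures.
- If the schools differ in change, leaving school out can make the test somewhat conservative. That offset would be accidental.
- Attitudes, normative beliefs and media literacy are average scores, to which a test of proportions does not apply without a cut-off. The simulation covers susceptibility only.
- Efficacy is disclaimed, and no significance level or decision rule is attached to these tests. This limits the consequence but does not remove it, because the tests are still planned.

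**Conclusion.** The concern holds. Classes are randomised, the single between-arm analysis is a student-level test, and nothing in the plan accounts for class. That mismatch is certain; the amount of inflation is not. For a 5% test of mean change with 32.5 students per class, the error is 5.0% if change does not vary between classes, about 9% at an ICC of change of 0.01 and about 22% at 0.05. Other readings of the test run from conservative to 16.5% in the scenarios tabulated. All of this rests on assumed ICCs, level and class size. The effect is confined to the secondary outcomes, so this should be fixed but does not threaten the trial's primary aim.

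**What to change.** Replace the two-sample tests with text such as: *For each secondary outcome and interval, one change per class will be computed among students with both assessments (change in proportion susceptible; mean change for the scales). The 8 class summaries will be regressed on arm and school (5 degrees of freedom; multiplier 2.57). The arm difference will be reported with its 95% CI, and no significance claim will be made.*

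For susceptibility, the intervals should be those the NOTE leaves in the plan. School is included because allocation was within school; 8 classes less 3 fitted terms leave 5 degrees of freedom. If no formal comparison is wanted, delete the test and report changes descriptively by arm and class, which suits a plan that says efficacy cannot be determined.

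**Cost.** No new data are needed. The NOTE is in the past tense, so some results may need re-analysis. Intervals will be wider than the student-level test implies, by a factor of (2.571/1.96) × √DEFF: about 1.3 if change does not vary between classes, 1.5 at an ICC of change of 0.01 and 2.1 at 0.05.

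### Classes are randomised within school, but the secondary between-arm comparison leaves school out: a small loss in the test as written, a larger one if the analysis moves to class level

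*Combined protocol and SAP*

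**What the plan says.** Under Methods, Randomization: "in each school, two classes will be randomized to the intervention condition and two classes to usual education". School is therefore the randomisation stratum, and there are eight classes, four per arm. Under Sample and Recruitment, the schools are picked to differ: "One school will be located in a rural area and the other will be located in a suburban area". Under Control Condition, the comparator is whatever a school normally teaches, introduced with "Many schools develop their own substance use prevention programming".

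The Statistical Analysis Plan, under Secondary Outcomes, compares changes in susceptibility, attitudes, normative beliefs and media literacy "between the intervention and control groups using two-sample tests of proportion". It names no stratification by school, school covariate, school-specific result or class term. It does not use the word pooling, but a single two-group test without a school term pools the schools.

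The sample-size paragraph plans "a sample size of 130 students (65 in each condition) in each school". The same SAP section states that a pilot cannot determine efficacy, and it sets no effect size, power or alpha for this comparison.

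**The concern.** An analysis should normally reflect the strata used in the randomisation. Leaving school out can do two things here.

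- **Leak.** A 2:2 allocation balances the number of classes, not of students. Class size, parental opt-out, absence and loss can give the two arms different school mixes. Part of any school difference in change then appears as an arm difference.
- **Lost precision.** Even with balanced arms, the school difference stays in the error term, and the standard error is larger than the design requires.

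In addition, one pooled number averages over two schools whose usual programmes may differ, without showing whether the contrast is similar in both. The data are meant to inform a later large trial, so that is worth seeing.

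**Working it through.** **1. The plan's own figure.** The only stated precision is a 95% interval width of 0.17 at a rate of 60%. With n = 130 (one school, both arms): 2 × 1.96 × √(0.6 × 0.4 / 130) = 0.168. It reproduces as a per-school figure. With 65 students the width would be 0.238, and with 260 it would be 0.119. It concerns feasibility, so the plan has no figure for the between-arm comparison.

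**2. Inputs.** From the documents: two schools, two classes per arm in each, 65 students per arm per school, mean class size 130/4 = 32.5. Assumed, because the documents give none: school rates of 25/35%, 20/40% and 15/45%; class sizes uniform on 22 to 40; pre-post correlation 0.5, so a change score has variance 2(1 − 0.5) = 1 SD²; class variance in change 0.01 SD². There is no true intervention effect throughout.

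**3. Student-level test, planned 65:65.** The school mix is the same in both arms, so the difference is unbiased. The pooled SE is √(0.30 × 0.70 × 2/130) = 0.0568 for each pair of rates. The stratified SE uses the mean within-school variance:

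| School rates | Mean p(1−p) | Stratified SE | Excess of pooled SE | True size of 5% test |
|---|---|---|---|---|
| 25/35% | 0.2075 | 0.0565 | 0.6% | 4.9% |
| 20/40% | 0.2000 | 0.0555 | 2.5% | 4.5% |
| 15/45% | 0.1875 | 0.0537 | 5.8% | 3.8% |

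For a change score with variance 1, a school gap g adds g²/4 to the variance. At 0.3 SD, √1.0225 = 1.011; at 0.4 SD, √1.04 = 1.020. The SE is 1% to 2% too wide. These figures treat students as independent within school.

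**4. Student-level test, unequal arms.** Leak fraction = (share of intervention students from one school) − (share of control students from that school).

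- 70:60 and 60:70: 70/130 − 60/130 = 0.077. For school gaps of 10, 20 and 30 points the estimate is off by 0.8, 1.5 and 2.3 points; true size 5.1%, 5.3% and 5.6%.
- 75:55 and 55:75: 75/130 − 55/130 = 0.154. It is off by 1.5, 3.1 and 4.6 points; true size 5.7%, 7.8% and 11.4%.

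A school-stratified difference is off by 0 in every case.

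**5. How large a leak is likely from class size alone.** In 400,000 draws of class sizes with 2:2 randomisation per school, the mean signed leak was zero, the mean absolute leak 5.1%, the median about 4% and the 95th percentile 12.3%. For an assumed 15-point gap in change, 0.051 × 15 = 0.8 points and 0.123 × 15 = 1.8 points (1.9 if the leak is taken as 12.5%).

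**6. Class-level analysis.** A class mean has variance 0.01 + mean(1/m) = 0.0433 SD². A school gap g adds 8 × (g/2)² = 2g² to the residual sum of squares if school is omitted. At 0.3 SD the expected residual mean square is (6 × 0.0433 + 0.18)/6 = 0.073 without school (6 df), against 0.0433 with school (5 df). Simulated mean 95% interval widths, in SD:

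| School gap in change | Without school | With school |
|---|---|---|
| 0 | 0.69 | 0.72 |
| 0.1 | 0.72 | 0.72 |
| 0.2 | 0.79 | 0.72 |
| 0.3 | 0.90 | 0.72 |
| 0.4 | 1.04 | 0.72 |

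Without school, the nominal 95% interval covers 98.4% at 0.3 SD; with school it covers 95%.

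**7. One school alone.** The difference rests on two classes per arm, so 2 df, and its 95% interval averages about 1.58 SD.

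**The case against.** The strongest objections concern size and relevance, and most of them stand.

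- **The large precision loss is not in the planned test.** A reader might take the 0.90 against 0.72 SD as the cost of the test as written. It is not: the SAP names a student-level test, for which the loss is about 0.6% to 5.8%. The larger figure applies only to a class-level analysis.
- **Large leaks are unlikely from class size.** A reader might picture 70/50 in one school and 50/70 in the other, where 70/120 − 50/120 = 17% of a school gap leaks, or 2.5 points of a 15-point gap. That was reached in 0.7% of the draws. The plan itself intends 65 per arm in each school.
- **This is not shown to be bias.** Class size is independent of the randomised arm, so the leak from it averages zero. Differential opt-out or loss could make it systematic. The SAP reports insufficient retention at one year, but gives no figures by arm or school, so a distorted result cannot be inferred.
- **Level is not change.** The SAP compares changes, so stable rural-suburban differences in level largely cancel. No document supports a particular school gap in change.
- **The comparator may be deliberate.** Usual programming is chosen to resemble a future trial. The documents do not say that these two schools' programmes differ, only that they may.
- **Class clustering is the larger omission.** With 32.5 students per class and an assumed ICC of 0.01 to 0.10, the design effect 1 + 31.5 × ICC runs from 1.32 to 4.15, and a nominal 5% test has size of about 9% to 34%. Adding school to a student-level test leaves that untouched.

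The last point shapes the repair but does not remove the need for it. Once the analysis respects class, the omitted stratum matters more, because only eight units carry the error term.

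**Conclusion.** The mismatch is real: the design stratifies by school and the comparison does not. For the planned student-level test the consequence is small. With 65:65 there is no bias and a standard error about 0.6% to 5.8% too wide for school rates from 25/35% to 15/45%. With unequal class sizes, typically about 5% of any school gap in change enters the estimate, and 12% at the 95th percentile, as chance imbalance. In a class-level analysis the loss is material if the schools differ in change by 0.2 SD or more, absent at 0.1 SD, and reversed (about 4% wider with school) if they do not differ.

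All of these sizes rest on assumed class sizes, school rates, school gaps and class variance. The primary feasibility outcome has no between-arm test and is unaffected. The comparison is exploratory and no decision rule uses it, so severity is low.

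**What to change.** In the SAP, under Secondary Outcomes, state that the between-arm comparison includes school as a fixed factor because it is the randomisation stratum, within an analysis that also respects class. One workable form is a linear model on the eight class-level means of change with arm and school, giving 5 df for the arm effect. School should not be added to a student-level test on its own. Averaging two school-specific differences is not the same as a fixed school factor at student level when sizes are unequal, so the SAP should name one method and its weights.

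Show the two school-specific differences beside the adjusted estimate, labelled as descriptive. Report the students analysed by arm, class and school, so that a reader can see any imbalance.

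The cost is a sentence or two in the SAP and one degree of freedom, about 4% in interval width if the schools do not differ in change. No new data are needed.

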Feasibility Metrics. (Primary Outcome). Data for the assessment of feasibility will be descriptive with point estimates and 95% confidence intervals. **One highly important quantitative outcome to inform a subsequent cluster randomized trial is overall retention of students.** Therefore, our main outcome of feasibility will be determined by at least 60% of students completing the pre-test, post-test, and both follow-up assessments, consistent with previous research. Other feasibility outcomes and related cut-offs are presented in **Table 1**.

Acceptability Metrics. Intervention participants will be asked to complete a series of acceptability items on the post-test assessment via close-ended 5-point Likert-type items (**Table 1**). These items are as follows: (1) I enjoyed *AD IT UP*, (2) I understood *AD IT UP*, (3) *AD IT UP* was easy to use, (4) I tried my hardest when I was doing *AD IT UP*, (5) I think *AD IT UP* would be helpful to other kids my age, (6) I would recommend *AD IT UP* to a friend, and (7) I agree with *AD IT UP*'s message.

Secondary Outcomes. Although efficacy cannot be assessed through this pilot trial, we include as part of all assessments quantitative items that will be used in a future RCT (**Table 1**), which include

susceptibility to future use of tobacco products, attitudes toward tobacco products, normative beliefs about tobacco products, and tobacco-related media literacy. These will be assessed at all 4 assessments.

- Susceptibility. Susceptibility will be assessed by asking participants whether they would use each tobacco product if it was offered to them by their best friend. Responses were *Definitely Yes*, *Probably Yes*, *Probably No*, and *Definitely No*. Separate items assessed susceptibility for cigarettes, cigars/cigarillos, e-cigarettes, and hookah. Consistent with previous literature, a participant was considered susceptible to use of an NTP if they answered anything other than “*Definitely No*” for that product.

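### The 95% CI width of 0.17 for the primary feasibility outcome treats students as independent, although whole classes are randomized and the plan makes no allowance for clustering

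*Combined protocol and SAP*

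**What the plan says.** The Design section describes the study as clustered: "We will conduct a cluster randomized controlled trial (RCT) in two high schools". Under Methods, Randomization, "Each school will have 4 health classes", and in each school "two classes will be randomized to the intervention condition and two classes to usual education". Sample and Recruitment adds that all assessments "will be completed during regular class time".

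The primary outcome is the proportion of students who complete all four assessments, judged against a 60% cut-off (Feasibility Metrics; Table 1). On its analysis, Feasibility Metrics says: "Data for the assessment of feasibility will be descriptive with point estimates and 95% confidence intervals". It presents retention as important because it will inform a later trial: "subsequent cluster randomized trial is overall retention of students". The Statistical Analysis Plan gives only numbers and percentages for this outcome and does not mention an interval.

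Power & Sample Size Justifications takes 60% as the expected value and plans for "a sample size of 130 students (65 in each condition) in each school". The precision claimed for that number is that it "will afford the ability to estimate feasibility with a 95% confidence interval width of 0.17". No section mentions an ICC, a design effect, a clustered variance or a mixed model.

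**The concern.** Students in one class share a teacher, a timetable and the sessions in which assessments are taken. Completing all four assessments may therefore be correlated within class, and 130 students in four classes then carry less information than 130 independent students.

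The stated precision is the only place where the plan puts a number on how well its primary outcome will be estimated. If it is too optimistic, and if the reported interval is computed in the same way, those designing the later cluster trial will take retention to be better known than four or eight classes can make it. The level is also unclear: the sample-size sentence is per school, while Feasibility Metrics speaks of overall retention with a single cut-off.

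**Working it through.** **Inputs.** From the documents: completion 0.60; 130 students per school; 2 schools; 4 classes per school, 2 per arm. Derived: 130/4 = 32.5 students per class; 260 students and 8 classes in all. Assumed, because the documents give none: class ICC of 0.01, 0.02, 0.05 or 0.10.

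**1. The plan's figure.** Width = 2 × 1.96 × √(p(1−p)/n). With p = 0.6:
- n = 130: 0.168, which rounds to the stated 0.17
- n = 65: 0.238
- n = 260: 0.119

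So 0.17 is the per-school figure with no design effect. The arithmetic is right.

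**2. One school and both schools, normal multiplier.** Design effect (DEFF) = 1 + (32.5 − 1) × ICC. Width = 2 × 1.96 × √(DEFF × 0.24/n).

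| ICC | DEFF | One school: 130/DEFF | One school: width | Both schools: width |
|---|---|---|---|---|
| 0 | 1.00 | 130 | 0.168 | 0.119 |
| 0.01 | 1.315 | 98.9 | 0.193 | 0.137 |
| 0.02 | 1.63 | 79.8 | 0.215 | 0.152 |
| 0.05 | 2.575 | 50.5 | 0.270 | 0.191 |
| 0.10 | 4.15 | 31.3 | 0.343 | 0.243 |

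Relative to 0.168, the one-school widths are 15%, 28%, 60% and 104% larger.

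**3. Break-even for both schools.** (0.17/0.1191)² = 2.04, and (2.04 − 1)/31.5 = 0.033. Below that ICC the pooled normal-multiplier width stays under 0.17.

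**4. What a simple binomial interval would do.** This was simulated with 2 schools, 4 classes of 32 or 33 in each, beta-binomial completion at 60%, and classes treated as drawn from a wider population. At ICC 0.01, 0.02, 0.05 and 0.10, a nominal 95% interval covers about 91%, 88%, 78% and 66% for one school. For both schools it covers about 90%, 86%, 76% and 65% (94% at ICC 0).

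**5. An interval that follows the randomization.** Take class as cluster and school by arm as strata, giving 8 − 4 = 4 df. Average width = 2 × 2.776 × 0.940 × √(DEFF × 0.24/260), where 0.940 is the mean ratio of estimated to true standard error on 4 df. With no clustering this is 2 × 2.776 × 0.940 × 0.0304 = 0.159. At ICC 0.01, 0.02, 0.05 and 0.10 it is 0.182, 0.202, 0.254 and 0.323. Simulated coverage is about 95% throughout, including with arms at 50% and 70%.

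**6. Stratifying by school only (6 df).** With equal retention in both arms the average widths are 0.14, 0.16, 0.18, 0.23 and 0.29 (ICC 0 to 0.10). With arms at 50% and 70%, the difference between arms enters the variance: coverage is 97% to 99.7% and average width 0.24 to 0.35.

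**The case against.** **The target of inference.** If each school's four classes are all its health classes, and the interval describes only those classes, class effects are fixed. A simple binomial interval then covers 94% to 96% at every ICC from 0 to 0.10. The documents leave this reading open: one sentence gives each school four classes, while the eligibility criterion asks for at least four. The objection limits the point but does not remove it, because the stated use of the result is a later trial in other classes. That wider use would also call for school-to-school variation, which two schools cannot supply.

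**Silence, not a choice.** A reader might infer that the plan has chosen a simple binomial interval. It has not. Feasibility Metrics names no method, and the coverage figures above show only what would follow if that method were used.

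**Assumed ICCs.** Every ICC here is an assumption. The documents do not say how students are grouped at the 12-month assessment, and the class ICC for completing all four assessments could be near zero. For both schools together, 0.17 is conservative at low ICC (normal multiplier). This stands.

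**Limited consequence.** The outcome is descriptive and 60% is a point cut-off. A note under Secondary Outcomes reports insufficient retention at one year, so that follow-up appears to have taken place. This also stands and lowers the severity.

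**Conclusion.** The concern holds in a limited form. The stated width is an independence calculation in a class-randomized trial. For the one-school sample that it names, it understates the width by an amount that depends on an unknown ICC: 0.19 to 0.34 over the assumed range. This rests on three conditions: the interval is meant to reach beyond the classes studied, completion is positively correlated within class, and classes are of about equal size.

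Stronger readings are tempting but not supported. The figure is not miscalculated. The sample is not shown to be too small, since no precision target is set that more students would have to meet. Nor is 0.17 shown to be too narrow for both schools together: with a normal multiplier that needs an ICC above about 0.033, and the documents give no pooled width to compare.

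Severity is minor to should-fix. What can still be corrected is how the reported interval is computed and described.

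**What to change.** State the level and the method. For example: *The 95% CI for the proportion of students completing all four assessments, both schools together, will use class as the cluster, school by arm as strata, and a t reference on 4 df (8 classes minus 4 strata).*

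Restate the precision as a range. For example: *With about 260 students in 8 classes and 60% completion overall, the average 95% CI width is about 0.16 with no clustering, 0.18 at a class ICC of 0.01, 0.20 at 0.02, 0.25 at 0.05 and 0.32 at 0.10; the ICC is an assumption.* If per-school intervals are also given, cluster them by class and say that each rests on four classes.

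Stratifying by school alone (6 df) is slightly narrower only if retention is the same in both arms, which cannot be assumed in advance.

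**Cost.** Two sentences and a survey-type interval in Stata, the software the plan names; no extra students. The drawbacks should be stated with the result:
- On average the interval is wider than the binomial one (0.16 against 0.12 even with no clustering).
- With eight classes it is unstable, and in some samples it will be narrower than the binomial interval.
- It does not cover school-to-school variation.
- If completion is near 10%, its coverage falls to about 91% to 94% over ICC 0.01 to 0.10, still above that of the binomial interval.
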